4.3 Withdrawal Procedures

Individual participants will be withdrawn from the study if they indicate they do not wish to participate (i.e., refuse or withdraw their consent), or if they cannot comply with the study procedures, such as not arriving at the laboratory to complete the shopping task or not being willing to select products in the mock store.

5 STUDY EVALUATIONS AND MEASUREMENTS

Outcome variables, organized by type (i.e., primary, secondary, other), are described in **Table 2**. Purchase variables (i.e., number of calories purchased from SSBs, number of calories purchased from all foods and beverages, proportion of participants who purchased an SSB, and number of SSBs purchased) are assessed by the experimenter, who records all of the participant's selections at the end of the shopping task. All other outcomes are assessed via participant self-report on a computer-based survey that is completed within ~30 minutes of completing the ~10-minute shopping task.

Table 2. Outcome variables.

| Outcome | Definition/Description | Timing of Assessment |
|---|--|---|
| Primary Outcome | | |
| Number of calories (kcal) purchased from SSBs | Total number of calories from sugar-sweetened beverages in the participant's basket when he/she completes the shopping task, calculated as the sum of calories/container for all SSB containers. | Immediately after the participant completes the ~10-minute shopping task. |
| Secondary Outcomes | | |
| Number of calories (kcal) purchased from all foods and beverages. | Assessed as the total number of calories from all products (including sugar-sweetened beverages, non-sugar-sweetened beverages, and all foods) in the participant's basket when he/she completes the shopping task. Total calories purchased will be calculated as the sum of calories/container for all products. | Immediately after the participant completes the ~10-minute shopping task. |

| Outcome | Definition/Description | Timing of Assessment |
|--|--|---|
| Proportion of participants who purchased a sugar-sweetened beverage | Assessed as the proportion of participants who have one or more sugar-sweetened beverage in his/her basket when he/she completes the shopping task. | Immediately after the participant completes the ~10-minute shopping task. |
| Number of sugar-sweetened beverages purchased | Assessed as the number of sugar-sweetened beverages in the participant's basket when he/she completes the shopping task. | Immediately after the participant completes the ~10-minute shopping task. |
| Mean intentions to limit consumption of beverages added sugar | Assessed using 3 items adapted from Klein, Zajac & Monin (2009). ⁵⁹ The items ask participants to rate the extent to which they want to, plan to, and are likely to, drink less than 1 beverage with added sugar in the next week. Responses to these three items will be averaged to create a mean intentions score. Response options are on a 1 to 7 scale, with higher scores indicating higher intentions to limit consumption of beverages with added sugar. | Within 30 minutes of completing ~10-minute shopping task |
| Mean intentions to limit consumption of specific sugar-sweetened beverages | Assessed using 5 items adapted from Klein, Zajac & Monin (2009). ⁵⁹ For each of the five beverage categories, participants will rate the extent to which they are likely to drink less than 1 serving of the beverage in the next week. Responses will be averaged to a create a mean intentions score. Response options are on a 1 to 7 scale, with higher scores indicating higher intentions to limit consumption of these beverages. | Within 30 minutes of completing ~10-minute shopping task |
| Proportion of participants who notice the trial labels | Assessed using 1 item adapted from Roberto et al. (2016). ¹⁹ The item asks participants to indicate whether they noticed the trial labels. Response options are 0 (no) and 1 (yes). | Within 30 minutes of completing ~10-minute shopping task |
| Mean attention to the trial labels | Assessed using 2 items adapted from Nonnemaker et al. (2010). ⁶⁰ The items ask participants to rate their agreement with statements about whether the label grabbed their attention and whether they read and looked closely at the label. Responses will be averaged to create a mean attention score. Responses are on a 1 to 5 scale, with higher scores indicating higher attention to the labels. | Within 30 minutes of completing ~10-minute shopping task |

| Outcome | Definition/Description | Timing of Assessment |
|---|--|--|
| Mean emotional reactions to trial labels | Assessed using 6 items adapted from Brewer et al. (2018). ⁶¹ The items ask participants to indicate the extent to which trial labels elicited particular emotional reactions (e.g., fear, guilt, disgust). Responses will be averaged to create a mean emotional reactions score. Response options are on a 1 to 5 scale, with higher scores indicating stronger emotional reactions. | Within 30 minutes of completing ~10-minute shopping task |
| Mean cognitive elaboration | Assessed using 2 items adapted from Moodie, MacKintosh & Hammond (2010) ¹⁶ and Fathelrahman et al. (2010). ⁶² Items ask participants to rate the amount they thought about the information conveyed by the trial label and about the health consequences of consuming beverages with added sugar. Responses will be averaged to create a mean cognitive elaboration score. Response options range from 1 to 5, with higher scores indicating more elaboration. | Within 30 minutes of completing ~10-minute shopping task |
| Social interactions about the labels | Assessed using 1 item adapted from Brewer et al. (2018). ⁶¹ Participants rate the extent to which they are likely to have social interactions about the trial label. Response options are on a 1 to 5 scale, with higher scores indicating a higher likelihood of having social interactions. | Within 30 minutes of completing ~10-minute shopping task |
| Mean perceptions of added sugar content in specific sugar-sweetened beverages | Assessed using 5 items adapted from Roberto et al. (2016). ¹⁹ For each of five beverage categories, participants rate the amount of added sugar they think is in 1 serving of the beverage. Responses will be averaged to create a mean perceptions of added sugar score. Response options are on a 1 to 4 scale, with higher scores indicating perceptions of higher added sugar content. | Within 30 minutes of completing ~10-minute shopping task |
| Mean attitudes toward consuming specific sugar-sweetened beverages | Assessed using 5 items adapted from Bollard et al. (2016). ¹⁸ For each of five beverage categories, participants rate how healthy/unhealthy it is for them to consume that beverage category. Responses will be averaged to create an mean attitudes score. Response options are on a 1 to 7 scale, with higher scores indicating more positive attitudes toward consuming these sugar-sweetened beverages. | Within 30 minutes of completing ~10-minute shopping task |

| Outcome | Definition/Description | Timing of Assessment |
|---|---|--|
| Mean product attitudes toward specific sugar-sweetened beverages | Assessed using 10 items adapted from Bollard et al. (2016). ¹⁸ For each of five beverage categories, participants rate the appeal and the coolness of the beverage category. Responses will be averaged to create a mean product attitude score. Responses are on a 1 to 7 scale, with higher scores indicating more positive product attitudes toward these sugar-sweetened beverages. | Within 30 minutes of completing ~10-minute shopping task |
| Mean outcome expectations regarding consumption of beverages with added sugar | Assessed using 4 items adapted from Roberto et al. (2016). ¹⁹ Participants will rate the extent to which they expect that consuming beverages with added sugar would increase their risk of negative health outcomes (e.g., tooth decay). Responses will be averaged to create a mean outcome expectations score. Responses are on a 1 to 7 scale, with higher scores indicating more negative outcome expectations. | Within 30 minutes of completing ~10-minute shopping task |
| Other Outcomes | | |
| Mean injunctive norms regarding consumption of beverages with added sugar | Assessed using 3 items adapted from Zoellner et al. (2012). ²¹ Items ask participants to rate the extent to which people who are important to them think they should drink less than 1 beverage with added sugar per week, would approve of them drinking less than 1 beverage with added sugar per week, and want them to drink less than 1 beverage with added sugar per week. Responses will be averaged to create a mean injunctive norms score. Responses are on a 1 to 5 scale, with higher scores indicating higher injunctive norms. | Within 30 minutes of completing ~10-minute shopping task |
| Perceived message effectiveness of trial label | Assessed using 1 item adapted from Brewer et al. (2018). ⁶⁰ Participants rate the extent to which the trial label to which they were exposed in the shopping task would discourage them from drinking beverages with added sugar. Response options are on a 1 to 5 scale, with higher scores indicating higher perceived message effectiveness. | Within 30 minutes of completing ~10-minute shopping task |
| Support for sugar-sweetened beverage health warning labels | Assessed using 1 item adapted from Brewer et al. (2018). ⁶⁰ Participants rate their support for a policy that would require health warning labels on sugar-sweetened beverages. Responses are on a 1 to 4 scale, with higher scores indicating greater support. | Within 30 minutes of completing ~10-minute shopping task |

| Outcome | Definition/Description | Timing of Assessment |
|--|--|--|
| Mean self-efficacy to limit consumption of beverages with added sugar | Assessed using 3 items adapted from Brewer et al. (2018). ⁶⁰ Items ask participants to rate the extent to which: it would be easy to drink less than 1 beverage with added sugar per week; they have the ability to drink less than 1 beverage with added sugar per week; and they are confident that they could drink less than 1 beverage with added sugar per week. Responses will be averaged to create a mean self-efficacy score. Responses are on a 1 to 5 scale, with higher scores indicating self-efficacy. | Within 30 minutes of completing ~10-minute shopping task |
| Mean response efficacy of limiting consumption of beverages with added sugar | Assessed using 5 items adapted from Brewer et al. (2018). ⁶⁰ Participants indicate the extent to which drinking no beverages with added sugar would lower their chances of weight gain, diabetes, tooth decay, and heart disease, and the extent to which drinking no beverages with added sugar would improve their health. Responses will be averaged to create a mean response efficacy score. Responses are on a 1 to 5 scale, with higher scores indicating greater response efficacy. | Within 30 minutes of completing ~10-minute shopping task |

6 STATISTICAL CONSIDERATIONS

General principles and analysis populations. We will use a two-sided critical alpha of 0.05 to conduct all statistical tests. All confidence intervals presented will be 95% and two-sided. Analyses of the primary, secondary, and other outcomes will include all randomized participants according to the trial arm they were randomized to receive. We will use complete case analysis to handle any missing data in analyses of the primary, secondary, and other outcomes.

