| Subject Population key criteria for Inclusion and Exclusion: | 
Inclusion Criteria
 
 1. Age 18 and older 2. Consume at least 1 serving (12 ounces) of sugar-sweetened beverages per week 3. Able to read and write in English 
Exclusion Criteria
 
 1. Under the age of 18 2. Consume less than 1 serving (12 ounces) of sugar-sweetened beverages per week 3. Unable to read and/or write in English |
| Number of Subjects | 400 |
| Study Duration | Each subject's participation will last approximately 30 minutes. The enrollment period is expected to last ~6 months. |
| Study Phases | 
There are two phases:
 
 (1) Screening: screening for eligibility and obtaining consent and (2) Intervention: study intervention/experimental treatment. |
| Efficacy Evaluations | The primary outcome is the total number of calories from sugar-sweetened beverages the participant purchases during the study shopping task, calculated as the sum of calories/container across all sugar-sweetened beverages in the participant's basket at the completion of the shopping task. |
| Statistical and Analytic Plan | 
Primary outcome
 
 • We will use ordinary least squares (OLS) regression to examine whether the primary outcome differs by trial arm, controlling for any participant characteristics found to be unbalanced across trial arms in balance tests. The coefficient on the trial arm indicator variable is the primary effect estimate, and gives the average difference in (adjusted) means between the treatment arm and the control arm. It is interpreted as the impact of SSB health warnings on total calories of sugar-sweetened beverages purchased. 
Secondary outcomes
 
 • We will use OLS regression, logistic regression, and Poisson regression to examine whether continuous, dichotomous, and count secondary outcomes differ by trial arm, respectively. |
| Data and Safety Monitoring Plan | 
 • The principal investigator is responsible for data quality management and ongoing assessment of safety. |

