4 STUDY PROCEDURES

4.1 Screening Procedures

Eligible participants are English-speaking adults age 18 years or older who consume at least one serving (12 ounces) of SSBs per week. Participants must be willing and able to consent and comply with study procedures. This study does not employ any exclusions based on race, ethnicity, or gender. To determine eligibility, interested participants are asked to complete a brief online survey. The survey queries the prospective participant's age, usual SSB consumption (using an adapted version of the BEV-Q 15, a validated questionnaire⁵⁸), and own and parental educational attainment. Participants aged 18 years or older who consume at least 12 ounces of SSBs per week are invited to schedule a time to participate. Ineligible participants are thanked for their time.

We will track and summarize participant enrollment, allocation, and analysis using a CONSORT diagram. The diagram will report the number of participants who were:

- Assessed for eligibility
- Excluded after screening
 - Excluded because did not meet inclusion criteria
 - Excluded because declined to participate or study visit never scheduled
 - Excluded because cancelled or did not attend study visit
- Randomized
- Received allocated intervention (by treatment arm)
- Analyzed (by treatment arm)
 - Withdrawn and/or excluded from analyses (and reason for exclusion)

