6.3 Statistical Methods

Data preparation and balance tests. To prepare the data, we will first examine all scales to ensure adequate internal consistency (i.e., Cronbach's alpha > 0.70), dropping items as needed to improve consistency. If we are unable to achieve adequate internal consistency by dropping items, we may exclude the unreliable scales from analyses (e.g., not analyze treatment effects on these outcomes).

Next, we will conduct balance tests. Specifically, we will report participants' age, gender, sexual orientation, Hispanic ethnicity, race, educational attainment, health literacy, household income, usual sugar-sweetened beverage consumption, and overweight status (body mass index [BMI] ≥ 25 kg/m²) by trial arm. We will summarize categorical variables as counts and percentages and continuous variables as means and standard deviations. The denominator for each percentage will be the number of participants within each treatment group, less any participants with missing data on the variable of interest. We will use *t*-tests and χ^2 tests to examine whether participants assigned to the trial arms differ on any continuous or categorical characteristics, respectively. We will report *p* values from these balance tests. Subsequent analyses will control for any unbalanced characteristics.

Analysis of the primary outcome (Efficacy analysis). We will use ordinary least squares regression (OLS) to examine whether the primary outcome differs by trial arm. Specifically, we will fit the following:

$$SSB \text{ calories purchased} = \beta_0 + \beta_1 \text{WARNING} + X\beta \quad (\text{Eq. 1})$$

Here, *SSB calories purchased* is the total calories from SSBs the participant had in her basket when she completed her shopping task, calculated as described in Table 2. WARNING is an indicator variable for whether the participant was in the health warning arm (WARNING = 1) or the control arm (WARNING = 0). We denote *X* as a vector of any participant characteristics (e.g., age, gender, race/ethnicity) found to be unbalanced across trial arms in balance tests.

The coefficient on WARNING (β_1) is the primary effect estimate, and gives the average difference in (adjusted) means between the treatment arm and the control arm. It is interpreted as the impact of SSB health warnings on total calories of SSBs purchased.

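### Complete-case handling of Eq. 1 would drop participants with recorded SSB calories if a characteristic flagged as unbalanced has blanks; the loss is conditional and small, and cheap to avoid

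*Combined protocol and SAP*

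**What the plan says.** Section 6 (general principles and analysis populations) defines the population: "Analyses of the primary, secondary, and other outcomes will include all randomized participants according to the trial arm they were randomized to receive". The next sentence gives the missing-data rule: "We will use complete case analysis to handle any missing data in analyses of the primary, secondary, and other outcomes". It makes no separate provision for covariates.

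Section 6.3 tests ten participant characteristics for balance between arms and then says: "Subsequent analyses will control for any unbalanced characteristics". In Eq. 1 these form the vector X. The same X enters the models for the other outcomes. Section 6.3 also foresees blanks in these characteristics, since its percentages use each arm's count "less any participants with missing data on the variable of interest". The plan specifies no imputation of X and no unadjusted version of Eq. 1.

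The primary outcome does not depend on the survey. Section 5 says that purchases are assessed by the experimenter, "who records all of the participant's selections at the end of the shopping task", and the synopsis sums the calories of the sugar-sweetened beverages (SSBs) "in the participant's basket at the completion of the shopping task".

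The screener in Section 4.1 covers "age, usual SSB consumption (using an adapted version of the BEV-Q 15") and "own and parental educational attainment". That accounts for three of the ten tested characteristics.

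**The concern.** Taken together, these rules let a blank covariate remove an observed primary outcome. Who enters the primary analysis would then depend on a chance imbalance and on whether a questionnaire item was answered, rather than on whether SSB purchases were observed.

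Age and usual SSB intake decide eligibility, so they should be known for everyone enrolled. Seven tested characteristics are not in the screener list: gender, sexual orientation, Hispanic ethnicity, race, health literacy, household income and overweight status. Section 11 says that the visit survey covers personal characteristics, and Section 4.2 places that survey after the shopping task. It is therefore a reasonable inference, though not stated, that these seven are collected after label exposure and after the basket has been recorded.

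What is at stake is mainly precision. The sample size has little slack, so even a modest number of dropped rows takes power below the planned 80%. The other three purchase outcomes (total calories, any SSB purchased, number of SSBs) are also recorded by the experimenter and use the same X, so they are exposed in the same way.

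**Working it through.** **Inputs from the documents.** f² = 0.02, two-sided alpha 0.05, 80% power, required N 395, enrolment 400 (Section 6.4); 1:1 allocation (Section 3.2); alpha 0.05 for all tests, hence also the balance tests (Section 6). **Assumed:** the blank rate on a flagged characteristic, shown as a range.

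**1. The plan's own figure.** For one regression coefficient, use the noncentral F distribution with 1 and N − 2 degrees of freedom and noncentrality λ = f² × N. The smallest N with power of at least 80% is 395 (power 80.06%), so the stated figure reproduces. At 400, power is 80.56%. With equal arms, f² = 0.02 corresponds to d = 2 × √0.02 = 0.283.

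**2. The allowance.** 400 − 395 = 5 participants, or 5/400 = 1.25%, for all missing data and incomplete visits.

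**3. Power if a flagged characteristic has blanks.** N = 400 × (1 − blank rate); standard error ratio = √(400/N).

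| Assumed blanks | N in Eq. 1 | Power | Standard error ratio |
|---|---|---|---|
| 0% | 400 | 80.6% | 1.000 |
| 1.25% | 395 | 80.1% | 1.006 |
| 2% | 392 | 79.8% | 1.010 |
| 5% | 380 | 78.5% | 1.026 |
| 10% | 360 | 76.3% | 1.054 |

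Two flagged characteristics with independent 5% blanks leave 400 × 0.95² = 361 participants and power of 76.4%.

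**4. How often the condition arises.** Under proper randomization, the chance that at least one of the seven non-screener characteristics is flagged at 0.05 is 1 − 0.95⁷ = 30.2% if the tests are independent, and 5% if they are fully correlated. Treating a flag as one characteristic with the assumed blanks:

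- 5% blanks: the loss is 80.56 − 78.52 = 2.04 points. Averaged over all trials it is 2.04 × 0.05 = 0.1 to 2.04 × 0.302 = 0.6 points.
- 10% blanks: the loss is 80.56 − 76.30 = 4.26 points, or 0.2 to 1.3 points on average.

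**5. Comparing remedies in the case that matters.** Simulation with 200 per arm and a true effect of −0.283 SD, keeping only runs in which the covariate is flagged at 0.05. Blanks are completely at random and the covariate–outcome correlation is 0.2 (both assumed).

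| | 5% blanks | 10% blanks |
|---|---|---|
| Power, complete case | 79.2% | 78.2% |
| Power, pooled-mean fill | 81.7% | 82.3% |

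Pooled-mean fill also has the lower root mean squared error, and its type I error is about 5%. Leaving the flagged covariate out gives a root mean squared error of about 0.108, against 0.101 to 0.102, and 6.6% to 7.2% false positives under the null.

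**6. Why no missing indicator.** As a stress test only, suppose that blanks occur solely among above-median purchasers in the warning arm and that the covariate is unrelated to the outcome. With 10% blanks in that arm and a true effect of −0.283, the mean estimate is −0.371 for complete case, −0.371 for fill plus indicator, and −0.282 for fill alone. When blanks fall in one arm only, the indicator absorbs those participants and so acts like deleting them.

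**The case against.** The strongest reply is that this hardly matters. In 70% to 95% of trials none of the seven characteristics is flagged, so none of them costs anything. Data come from one short visit with a computer-based survey and no follow-up, so blanks may be rare: at 1.25% power is still 80.1%, and at 2% it is 79.8%. The 5% and 10% rates are assumptions, and the timing of the seven characteristics is inferred. All of this stands and sets the severity. It does not remove the point, because the stated rule discards observed outcomes when a nearly free alternative keeps them.

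A second objection concerns the remedy. Restricting adjustment to the screener variables would avoid most blanks, but it changes covariate selection and does worse once another covariate is flagged (step 5). Nor should filling extend to a blank moderator in Eq. 2, where a pooled proportion has no sensible meaning in an interaction. Both objections are right, and the fix respects them.

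A reader might infer more than the documents support:

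- *That the primary estimate will be biased.* Complete-case analysis is unbiased if blanks are completely at random. Bias would need blanks that depend on arm and purchases, and nothing in the documents shows this. The stress test in step 6 is an invented mechanism, used only to choose between remedies.
- *That the plan has no rule, or flatly contradicts its all-randomized population.* It has a rule, and the complete-case sentence directly follows and qualifies the population sentence. For missing outcomes that qualification is reasonable.
- *That the sample size is wrong.* The 395 reproduces exactly.

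**Conclusion.** The point holds as a minor one. Under the plan's own wording, a participant with recorded SSB calories leaves Eq. 1 if a characteristic flagged as unbalanced is blank. When that happens, the cost is about 1, 2 or 4 points of power at an assumed 2%, 5% or 10% blanks. Averaged over the chance of a flag, it is at most about 1.3 points at 10%. If no characteristic is flagged, or the flagged one is complete, nobody is lost.

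The sizes rest on the assumed blank rates, on f² = 0.02 as the true effect, on all 400 baskets being recorded, and on the inference that the seven non-screener characteristics come from the survey after shopping. The mechanism itself rests only on the text of Sections 5, 6 and 6.3.

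**What to change.** Amend the wording of Sections 6 and 6.3 before the data are examined:

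- State that Eq. 1, and the models for the other three experimenter-recorded purchase outcomes, include every randomized participant with a recorded basket, analysed in the assigned arm.
- Fill a blank in an adjustment covariate in X with the mean pooled over both arms, or the pooled proportion for each category of a categorical variable. Do not add a missing indicator.
- Keep complete-case handling for missing outcomes and for a blank moderator in Eq. 2.
- Report by arm the number with a recorded basket, the number analysed and the number of filled values for each covariate.
- Leave the selection of covariates as planned. Do not restrict adjustment to the screener variables.

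This needs no new data and a few lines of code. The small downside is a slightly imperfect adjustment for the few participants with a filled value.
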